# 15.1 IRB and/or IEC Approval

IRBs and IECs must be constituted according to the applicable state and federal/local requirements of each participating region. The sponsor or designee will require documentation noting all names and titles of members who make up the respective IRB or IEC. If any member of the IRB or IEC has direct participation in this study, written notification regarding his or her abstinence from voting must also be obtained. Those US sites unwilling to provide names and titles of all members due to privacy and conflict of interest concerns should instead provide a Federal Wide Assurance Number or comparable number assigned by the Department of Health and Human Services.

The sponsor or designee will supply relevant documents for submission to the respective IRB or IEC for the protocol's review and approval. This protocol, the Investigator's Brochure, a copy of the informed consent form, and, if applicable, subject recruitment materials and/or advertisements and other documents required by all applicable laws and regulations, must be submitted to a central or local IRB or IEC for approval. The IRB's or IEC's written approval of the protocol and subject informed consent must be obtained and submitted to the sponsor or designee before commencement of the study (ie, before shipment of the sponsor-supplied drug or study specific screening activity). The IRB or IEC approval must refer to the study by exact protocol title, number, and version date; identify versions of other documents (eg, informed consent form) reviewed; and state the approval date. The sponsor will [ship drug/notify site] once the sponsor has confirmed the adequacy of site regulatory documentation and, when applicable, the sponsor has received permission from competent authority to begin the trial. Until the site receives [drug/notification] no protocol activities, including screening may occur.

Sites must adhere to all requirements stipulated by their respective IRB or IEC. This may include notification to the IRB or IEC regarding protocol amendments, updates to the informed consent form, recruitment materials intended for viewing by subjects, local safety reporting requirements, reports and updates regarding the ongoing review of the study at intervals specified by the respective IRB or IEC, and submission of the investigator's final status report to IRB or IEC. All IRB and IEC approvals and relevant documentation for these items must be provided to the sponsor or its designee.

Subject incentives should not exert undue influence for participation. Payments to subjects must be approved by the IRB or IEC and sponsor.

Written consent documents will embody the elements of informed consent as described in the Declaration of Helsinki and the ICH Guidelines for GCP and will be in accordance with all applicable laws and regulations. The informed consent form, subject authorization form (if applicable), and subject information sheet (if applicable) describe the planned and permitted uses, transfers, and disclosures of the subject's personal and personal health information for purposes of conducting the study. The informed consent form and the subject information sheet (if applicable) further explain the nature of the study, its objectives, and potential risks and benefits, as well as the date informed consent is given. The informed consent form will detail the requirements of the participant and the fact that he or she is free to withdraw at any time without giving a reason and without prejudice to his or her further medical care.

The investigator is responsible for the preparation, content, and IRB or IEC approval of the informed consent form and if applicable, the subject authorization form. The informed consent form, subject authorization form (if applicable), and subject information sheet (if applicable) must be approved by both the IRB or IEC and the sponsor prior to use.

The informed consent form, subject authorization form (if applicable), and subject information sheet (if applicable) must be written in a language fully comprehensible to the prospective subject. It is the responsibility of the investigator to explain the detailed elements of the informed consent form, subject authorization form (if applicable), and subject information sheet (if applicable) to the subject. Information should be given in both oral and written form whenever possible and in the manner deemed appropriate by the IRB or IEC. In the event the subject is not capable of rendering adequate written informed consent, then the subject's legally acceptable representative may provide such consent for the subject in accordance with applicable laws and regulations.

The subject, or the subject's legally acceptable representative, must be given ample opportunity to: (1) inquire about details of the study and (2) decide whether or not to participate in the study. If the subject, or the subject's legally acceptable representative, determines he or she will participate in the study, then the informed consent form and subject authorization form (if applicable) must be signed and dated by the subject, or the subject's legally acceptable representative, at the time of consent and prior to the subject entering into the study. The subject or the subject's legally acceptable representative should be instructed to sign using their legal names, not nicknames, using blue or black ballpoint ink. The investigator must also sign and date the informed consent form and subject authorization (if applicable) at the time of consent and prior to subject entering into the study; however, the sponsor may allow a designee of the investigator to sign to the extent permitted by applicable law.

Once signed, the original informed consent form, subject authorization form (if applicable), and subject information sheet (if applicable) will be stored in the investigator's site file. The investigator must document the date the subject signs the informed consent in the subject's medical record. Copies of the signed informed consent form, the signed subject authorization form (if applicable), and subject information sheet (if applicable) shall be given to the subject.

Dexlansoprazole Capsules	
Study No. TAK-390MR_302	Page 65 of 82
Protocol Incorporating Amendment No. 03	20 February 2017

All revised informed consent forms must be reviewed and signed by relevant subjects or the relevant subject's legally acceptable representative in the same manner as the original informed consent. The date the revised consent was obtained should be recorded in the subject's medical record, and the subject should receive a copy of the revised informed consent form.

# **15.3** Subject Confidentiality

The sponsor and designees affirm and uphold the principle of the subject's right to protection against invasion of privacy. Throughout this study, a subject's source data will only be linked to the sponsor's clinical study database or documentation via a unique identification number. As permitted by all applicable laws and regulations, limited subject attributes, such as sex, age, or date of birth, and subject initials may be used to verify the subject and accuracy of the subject's unique identification number.

To comply with ICH Guidelines for GCP and to verify compliance with this protocol, the sponsor requires the investigator to permit its monitor or designee's monitor, representatives from any regulatory authority (eg, FDA, Medicines and Healthcare products Regulatory Agency, Pharmaceuticals and Medical Devices Agency), the sponsor's designated auditors, and the appropriate IRBs and IECs to review the subject's original medical records (source data or documents), including, but not limited to, laboratory test result reports, ECG reports, admission and discharge summaries for hospital admissions occurring during a subject's study participation, and autopsy reports. Access to a subject's original medical records requires the specific authorization of the subject as part of the informed consent process (see Section 15.2).

Copies of any subject source documents that are provided to the sponsor must have certain personally identifiable information removed (ie, subject name, address, and other identifier fields not collected on the subject's eCRF).

## 15.4 Publication, Disclosure, and Clinical Trial Registration Policy

## 15.4.1 Publication and Disclosure

The investigator is obliged to provide the sponsor with complete test results and all data derived by the investigator from the study. During the study, only the sponsor may make study information available to other study investigators or to regulatory agencies, except as required by law or regulation. Except as otherwise allowable in the clinical study site agreement, any public disclosure (including publicly accessible websites) related to the protocol or study results, other than study recruitment materials and/or advertisements, is the sole responsibility of the sponsor.

The sponsor may publish any data and information from the study (including data and information generated by the investigator) without the consent of the investigator. Manuscript authorship for any peer-reviewed publication will appropriately reflect contributions to the production and review of the document. All publications and presentations must be prepared in accordance with this section and the Clinical Study Site Agreement. In the event of any discrepancy between the protocol and the Clinical Study Site Agreement, the Clinical Study Site Agreement will prevail.

# 15.4.2 Clinical Trial Registration

In order to ensure that information on clinical trials reaches the public in a timely manner and to comply with applicable law, regulation and guidance, Takeda will, at a minimum register all clinical trials conducted in patients that it sponsors anywhere in the world on ClinicalTrials.gov or other publicly accessible websites before trial initiation. Takeda contact information, along with investigator's city, state (for US investigators), country, and recruiting status will be registered and available for public viewing.

For some registries, Takeda will assist callers in locating trial sites closest to their homes by providing the investigator name, address, and phone number to the callers requesting trial information. Once subjects receive investigator contact information, they may call the site requesting enrollment into the trial. The investigative sites are encouraged to handle the trial inquiries according to their established subject screening process. If the caller asks additional questions beyond the topic of trial enrollment, they should be referred to the sponsor.

Any investigator who objects to Takeda providing this information to callers must provide Takeda with a written notice requesting that their information not be listed on the registry site.

# 15.4.3 Clinical Trial Results Disclosure

Takeda will post the results of this clinical trial, regardless of outcome, on ClinicalTrials.gov or other publicly accessible websites, as required by applicable laws and/or regulations.

# 15.5 Insurance and Compensation for Injury

Each subject in the study must be insured in accordance with the regulations applicable to the site where the subject is participating. If a local underwriter is required, then the sponsor or sponsor's designee will obtain clinical study insurance against the risk of injury to clinical study subjects. Refer to the Clinical Study Site Agreement regarding the sponsor's policy on subject compensation and treatment for injury. If the investigator has questions regarding this policy, he or she should contact the sponsor or sponsor's designee.

Dexlansoprazole Capsules	
Study No. TAK-390MR_302	Page 68 of 82
Protocol Incorporating Amendment No. 03	20 February 2017

	Screening Period		Treatment Period				
	Screening	Study Day -1 Baseline	Study Day 1	Week 2 (a)	Week 4 or Final Visit (a)	Unscheduled Visit	Follow-up Phone Call (m)
Study Day/Week:	Days -21 to -2	Day -1	Day 1	Week 2	Week 4		Last dose+5 to 10 days
Visit Windows (Days):				±3	±3		v
Visit Number:	1	2		3	4		5
Informed consent	X						
Demographics/medical/social history	X						
Medication history	X						
Physical examination	X	Х		Х	X	X	
Concurrent medical condition(s)	X						
Vital signs, body weight and height	X(b)	Х		Х	X	X	
ECG	X				X		
Endoscopy	X (c)						
H. pylori serology	X						
Clinical laboratory tests	X (c)				X (d)		
Hepatitis panel(l)	X (c)						
Fasting serum gastrin (d)		Х			X	X	
Urine pregnancy test(k)	X	Х			X		
Serum hCG(k)	X	Х			X		
Serum FSH	X (e)						
Guidance on avoidance of pregnancy and ova and sperm donation	X	Х		Х	X		
IWRS randomization		Х					
First day of study drug			X				
Concomitant medication(s)	X	Х		Х	Х	X	
AEs assessment	Х	Х		Х	Х	X	Х
GERD symptoms investigator assessment		Х		Х	X	X	
Daily eDiary review/dispense (f)	X	X	X		X	>	
Dispense study drug via IWRS		X (g)		Х			
Study Drug return/accountability				X (h)	X		
Dispense rescue medication	X	X (i)		X (i)			
Rescue medication return/accountability		X (j)		X (j)	X		

# Appendix A Schedule of Study Procedures

Footnotes are on last table page.

Dexiansoprazole Capsules	
Study No. TAK-390MR_302	Page 70 of 82
Protocol Incorporating Amendment No. 03	20 February 2017

(a) Subjects who prematurely discontinue from the Treatment Period should undergo Final Visit procedures no later than 5 days after the last dose of study drug.

(b) Height is measured only at Screening.

(c) The screening clinical laboratory tests, hepatitis panel and endoscopy must be performed within 14 days prior to randomization. Any reliable, documented results available from an endoscopy performed in a routine clinical setting (before signing of informed consent) in the same institution will be accepted instead, given the invasive nature of the procedure.

(d) Except for Visit 1 (Screening Days -21 to -2), subjects should be fasting for a minimum of 8 hours prior to the specimen collection. During the study drug treatment period, subjects should be instructed to take their dose of study medication on the morning of their visit with a sip of water before specimen collection occurs. Breakfast should be eaten only after specimen collection.

(e) Only if menopause is suspected.

(f) Subjects should complete the eDiary every morning (for nighttime symptoms) and every evening (for daytime symptoms). The eDiary will be dispensed at Screening and reviewed at corresponding visit. eDiary needs to be checked carefully on Day -1 visit to assure the compliance and reeducate subjects accordingly if it's necessary.

(g) Study drug dispensed on Study Day -1 of the Screening Period Visit after the subject has completed all of the Screening Period procedures and subject has met all admission criteria for the study. Study drug will be self-administered on a daily basis for 4 weeks.

(h) Study drug will be returned at the Week 2 Visit for compliance verification.

(i) Rescue medication will be dispensed at Screening and may be dispensed at Study day -1 and Week 2 if needed.

(j) Rescue medication will be returned at Study day -1, Week 2 and Week 4 for accountability.

(k) Women of childbearing potential only. Baseline serum pregnancy test will not be needed if the screening pregnancy test is within 14 days of randomization.

(1) Hepatitis panel including HBsAg and HCV-antibody can be done either at the central laboratory or the local laboratory, depending on the site capability

(m) Follow-up phone call will occur for all subjects from 5 to 10 days after their last dose of study medication.

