# 6.0 STUDY DESIGN AND DESCRIPTION

# 6.1 Study Design

This is a phase 3, randomized, double-blind, multicenter, placebo-controlled, 2-arm study with a 4-week treatment period. This study will compare the efficacy of dexlansoprazole capsule (30 mg QD) with that of placebo when administered orally as a single daily dose in the morning, without regard to food. The study is designed to evaluate heartburn relief in subjects with symptomatic nonerosive GERD. Approximately 200 subjects, 18 years and above will be enrolled at approximately 20 sites across China.

The study consists of 2 periods: a Screening Period, which will last a maximum of 21 days, and a Treatment Period, which will last 4 weeks.

After signing an informed consent form (ICF), subjects will undergo a Screening Period. Subjects will be instructed that lifestyle or behavioral modifications designed to treat their symptoms of GERD should not be altered throughout the study.

During the Screening Period, subjects will undergo various procedures to determine eligibility for the Treatment Period. Screening evaluations will include the following: demographics, medical and social history, physical examination including vital signs, height and weight, ECG, endoscopy, clinical laboratory evaluations including hepatitis panel, urine and serum pregnancy test (all women subjects of childbearing potential), and concomitant medication assessment. The screening clinical laboratory tests, hepatitis panel, and endoscopy must be performed within 14 days prior to randomization. Subjects will be given rescue medication and eDiary on the first day of the Screening Period. Throughout the Screening Period, subjects will record their usage of rescue medication and document the presence and maximum severity of daytime and nighttime heartburn symptoms each day in their eDiary. Endoscopy data will be collected to exclude subjects with EE. Endoscopic pictures will be taken by the study site and kept in the site's source document files according to the site's practice. It may be collected by Takeda as necessary.

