Subjects who satisfy the screening evaluation and selection criteria may be entered into the study. Subjects who identified heartburn as their primary symptom, had a history of heartburn episodes for 6 months or longer, experienced heartburn on at least 4 of the 7 days preceding Study Day -1, and showed macroscopically normal esophageal mucosa at the Screening endoscopy, will be eligible for the Treatment Period in this study. Subjects having an esophageal stricture will be excluded from the study. The endoscope must pass freely into the stomach during the endoscopy. The rescue medication will be supplied during the screening period.

All subjects will return to the investigative site on Day -1, which will be deemed as the Baseline. Subjects who have completed all of the Screening procedures and met all eligibility requirements and none of the exclusion criteria will have routine fasting laboratory evaluations including fasting serum gastrin, a urine pregnancy test (all women subjects of childbearing potential), a physical examination and vital signs measurements to assure continued eligibility. In addition, subjects will be assessed for GERD symptoms such as heartburn, acid regurgitation, dysphagia, belching, and epigastric pain by investigator assessment.

Dexlansoprazole Capsules	
Study No. TAK-390MR_302	Page 22 of 82
Protocol Incorporating Amendment No. 03	20 February 2017

Subjects will be dispensed study drug on Day -1 according to an Interactive Web Response System (IWRS) and will begin taking study drug at the following day (Day 1). Rescue medication will continue to be supplied during the Treatment Period.

[figure not shown]
Subjects will be randomized in a 1:1 ratio to one of the following 2 treatment groups during the 4-week Treatment Period:

[figure not shown]
Group I: dexlansoprazole capsules (30 mg QD)

Group II: placebo (QD)

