- 9. The subject has a history of surgical procedures that may affect the esophagus (eg, fundoplication and mechanical dilatation for esophageal strictures) or a history of gastric or duodenal surgery other than endoscopic removal of benign polyps.
- 10. Subjects with EE as shown by endoscopy, during the Screening Period.
- 11. The subject has any abnormal laboratory value during screening or Day-1 that suggests a clinically significant underlying disease or condition that may prevent the subject from entering the study, based on the medical judgment of the investigator, or the subject has:
  - a) Creatinine >1.5 mg/dL or
  - b) Alanine aminotransferase (ALT) and/or aspartate aminotransferase (AST) >2.5 times the upper limit of normal (×ULN) or
  - c) Total bilirubin >2.0 mg/dL
- 12. The subject is known to have acquired immunodeficiency syndrome (AIDS) or hepatitis, including hepatitis virus carriers: (ie, hepatitis B surface antigen HBs-antigen (HBsAg) positive or hepatitis C virus (HCV)-antibody positive).
- 13. The subject has current Zollinger-Ellison syndrome or a history of gastric acid hypersecretion.
- 14. The subject is scheduled for surgery that requires hospitalization or requires surgical treatment during his/her participation in the study.

- 15. The subject has donated or lost >300 mL blood volume, undergone plasmapheresis, or has had a transfusion of any blood product within 90 days prior to the first dose of study drug.
- 16. The subject has a history of alcohol or drug abuse (defined as any illicit drug use), or drug addiction in the 12 months prior to Screening.
- 17. If the subject is a pregnant or lactating woman; is intending to become pregnant before, during, or within 30 days after participating in this study; is intending to donate ova during this time period; or is a man who is intending to donate sperm.
- 18. Any subject who, in the opinion of the investigator, is unable to comply with the requirements of the study or is unsuitable for any reason.
- 19. The subject with positive serology result of Helicobacter pylori (H. pylori) that needs eradication therapy during the study participation period as anticipated by the investigator.
- 20. The subject is an immediate family member, study site employee, is in a dependent relationship with a study site employee who is involved in conduct of this study (eg, spouse, parent, child, sibling), or may consent under duress.

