# 9.1.16 Endoscopy

During Screening Visit an endoscopy will be performed on all subjects to document the presence/absence of EE. Endoscopy should be performed while subjects are fasted and according to the usual practice of the institution (ie, with regard to premedications or concomitant therapies, as long as they are not prohibited in Section 1 of this protocol). Subjects with macroscopic normal esophagus will be eligible for the study.

The screening endoscopy must be performed within 14 days prior to randomization. Any reliable, documented results available from an endoscopy performed in a routine clinical setting (before signing of informed consent) in the same institution will be accepted, given the invasive nature of the procedure.

Any subjects with suspicious Barrett's esophagus seen during screening endoscopy will be excluded from the study. These Endoscopy assessments will be recorded on the eCRF and a copy of the results should be kept with the subject's notes. Digital images of the endoscopy should be captured and stored at the investigational site; images may be accessed by Takeda as necessary for quality assurance purpose.

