6.6 Medication History and Concomitant Medications

6.6.1 Medication History

The incidence of medication history was similar across the treatment groups. The most common of these medications were propofol (48.8%) and dyclonine hydrochloride (34.9%). The details of medication history information are listed in Table 15.1.11 and Appendix 16.2.4.4.

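### Appendix A footnote (c) lets a routine pre-consent endoscopy of any age replace the one required within 14 days, in conflict with section 6.1

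*Protocol*

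**What the plan says.** Protocol 6.1 states the window without exception: "The screening clinical laboratory tests, hepatitis panel, and endoscopy must be performed within 14 days prior to randomization". The procedure list in 9.3.1 and SAP 2.0 also give 14 days with no exception.

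Protocol 9.1.16 says "The screening endoscopy must be performed within 14 days prior to randomization". Its next sentence says that a reliable, documented endoscopy from routine practice, done "before signing of informed consent) in the same institution will be accepted, given the invasive nature of the procedure". The opening text of 9.3.1 has the same pair of statements.

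Appendix A footnote (c) begins "The screening clinical laboratory tests, hepatitis panel and endoscopy must be performed within 14 days prior to randomization". It then says that such a routine endoscopy, done "before signing of informed consent) in the same institution will be accepted instead, given the invasive nature of the procedure".

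Two eligibility statements depend on the endoscopy. Exclusion 10 in 7.2 reads "Subjects with EE as shown by endoscopy, during the Screening Period". Section 6.1 says that subjects who, among other conditions, "showed macroscopically normal esophageal mucosa at the Screening endoscopy, will be eligible for the Treatment Period in this study".

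On acid suppression, Table 7.a excludes PPIs and H2RAs during Screening and afterwards. Its NSAID row reaches back 30 days before Screening; its PPI and H2RA rows have no look-back.

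**The concern.** The title and the primary objective name a nonerosive population, and endoscopy is the only procedure in the schedule that establishes it. In footnote (c) the second sentence undoes the first: a result accepted *instead* of the dated one need not meet the date. Sites then hold two instructions for the same test, and the more permissive one sits in the schedule they work from.

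At stake is who is in the trial. Mucosa that was normal at an old endoscopy need not be normal at randomisation. If such subjects enter, the result applies to a population less sharply defined than the one stated, and a subject with current EE could be assigned to placebo.

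**Working it through.** No calculation in the plan depends on this point, so the check compares the passages.

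**1. What each place allows**

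| Place | 14-day rule | Pre-consent exception | Word *instead* | Maximum age of exception |
|---|---|---|---|---|
| Protocol 6.1 | yes | none | – | – |
| Protocol 9.1.16 | yes | yes | no | not stated |
| Protocol 9.3.1, opening text | yes | yes | no | not stated |
| Protocol 9.3.1, procedure list | yes | none | – | – |
| Appendix A, footnote (c) | yes | yes | yes | not stated |
| SAP 2.0 | yes | none | – | – |

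The exception requires the result to be reliable, documented and from the same institution. None of these limits age.

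**2. Whether the exception can work inside 14 days.** Appendix A puts Screening at Days -21 to -2 and randomisation on Day -1. A pre-consent endoscopy is at least as old at randomisation as the interval from consent to randomisation.

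- Consent on Day -21: 21 − 1 = 20 days. Consent on Day -16: 16 − 1 = 15 days. For consent on Days -21 to -16, any pre-consent endoscopy is outside the window.
- Consent on Day -15: 15 − 1 = 14 days. From here on the exception can fit. With consent on Day -8, for example, the interval is 7 days, which leaves 14 − 7 = 7 days before consent.

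The two readings therefore admit different subjects. Under one, the endoscopy is at most 14 days old; under the other it has no upper limit.

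**3. Whether another criterion closes the gap.** Taken literally, exclusion 10 covers EE seen during the Screening Period, and 6.1 refers to the Screening endoscopy. A pre-consent endoscopy is neither. Section 9.1.16 does require a macroscopically normal oesophagus, and 9.1.15 requires screening tests to be reviewed before randomisation. These act on whatever result is presented and do not make it recent.

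**4. PPI use, a separate gap.** Inclusion 5 requires symptoms that responded to acid suppression, so earlier use is expected. Section 4.1 says that PPIs heal injured mucosa and keep it healed. Because Table 7.a bars PPIs only from Screening, a normal endoscopy before Screening, or early in it, may follow recent PPI use. Section 9.1.2 records PPIs and H2RAs stopped at or within 90 days before consent, but no criterion uses that record. An age limit on the endoscopy would not close this gap.

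**The case against.** The strongest reply is that 9.1.16 and 9.3.1 lack *instead*. Read there, the sentence may waive only the rule that consent precedes procedures (9.1.1) and leave the 14 days intact. Step 2 shows that this reading is workable for consent on Day -15 or later. Amendment 03 also lengthened the endoscopy window to 14 days for flexibility, which suggests that the window was meant to bind. This shows a plausible intent. It does not remove *instead* from footnote (c), and it leaves sites with conflicting text.

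A second reply is that an accepted result stands in for the screening endoscopy, so EE seen on it would in practice exclude the subject. That is reasonable. What remains is loose wording in exclusion 10 and the missing age limit.

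A third is that randomisation would be expected to spread any misclassified subjects over both arms. That also stands: the point concerns who is studied and does not show a biased comparison between arms.

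A reader might infer wide use of the exception from SAP 6.6.1, where propofol, a likely endoscopy premedication, is in the medication history of 48.8% of subjects (0.488 × 215 ≈ 105). The documents do not support this.

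- SAP 6.6.2 also lists propofol among drugs started and stopped before baseline, in 54.2% of 107 and 54.6% of 108 subjects: 58 + 59 = 117. Since 105 + 117 = 222 exceeds 215, at least 7 subjects have both entries. A history entry therefore does not identify the qualifying endoscopy.
- Medication history includes drugs stopped at consent, so it can reflect endoscopies inside the 14 days.
- The 90-day medication-history period governs data capture. It is not a limit on endoscopy age.

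**Conclusion.** The point holds as an inconsistency in the eligibility rules. Footnote (c), read as written, permits an endoscopy of any age; 6.1 does not; 9.1.16 and 9.3.1 can be read either way. This rests on the text alone, on giving *instead* its ordinary meaning, and on the absence of an age limit anywhere.

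Its size is unknown. The documents do not report the age of any qualifying endoscopy, PPI use at that date, or the number of subjects who entered through the exception. A reader might conclude that the trial no longer answers its question for nonerosive GERD, or that the reported P=0.057 for the primary endpoint (SAP 7.1) reflects misclassified subjects. Neither follows: there may have been no such subjects, and the direction of any effect cannot be determined. Nor do the documents call for excluding anyone with previously documented EE, since section 4.1 defines nonerosive GERD by absence of endoscopically observed injury and not by history.

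**What to change.** 1. Reconcile footnote (c), 9.1.16 and 9.3.1 with the window in 6.1, so that a routine pre-consent endoscopy is accepted only if it falls within the 14 days before randomisation.
2. Word exclusion 10 to refer to EE at the qualifying endoscopy, whenever it was done.
3. Record in the eCRF the date of that endoscopy and PPI or H2RA use at that date. Section 9.1.16 already sends the endoscopy assessments to the eCRF, and 9.1.2 already collects much of the drug history. This makes the Table 7.a gap visible; whether that table needs a look-back is for the sponsor to settle.
4. Repeat the primary Wilcoxon rank-sum comparison, excluding subjects whose qualifying endoscopy was more than 14 days before randomisation or was done on a PPI. Both conditions are fixed before randomisation, so the comparison remains between randomised subjects. Label it post hoc: results are unblinded, and SAP 5.15 already reports one ad hoc analysis added afterwards. It should not replace the primary analysis.

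The cost is wording in a few places, two data items and one analysis. Some patients with an older routine endoscopy would need the screening endoscopy already scheduled, or would not enter. For the completed trial, only the retrieval of endoscopy dates and PPI use and the analysis apply; the wording serves any reuse of the protocol.
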